8 TRIAL ASSESSMENTS AND PROCEDURES

The Schedules of Activities for the Screening Period and Treatment/Observation Periods, including allowed visit windows, assessments, and procedures are detailed in:

- Table 1 Schedule of Activities: Screening Period
- Table 2 Schedule of Activities: Double-blind Intervention Period
- Table 3 Schedule of Activities: Long-term Extension Period

Guidelines for study procedures and assessments are discussed briefly in the following sections.

Consult the Study Reference Manual for additional information, including a recommended order of (specific) assessments for each visit.

8.1 Screening/Baseline Assessments

Screening for eligibility will be conducted using a tiered approach and may be completed over multiple days (see Section 4.1). The duration of the Screening Period may be up to 8 weeks to allow for the completion of assessments and for the evaluation of required laboratory, ECG, and imaging tests. If additional time is required this will be considered and approved on a case by case basis by the Sponsor Medial Monitor.

A non-contrast brain MRI is performed as the final test for eligibility. If a brain MRI or tau PET scan is not available within the screening window, the Screening Period may be extended, if all other eligibility criteria have been met, by up to 14 days to provide additional time for the imaging results to become available. If the screening window is extended for an individual, repeat clinical chemistry, hematology, and coagulation panels. Results of the repeated laboratory tests are to be reviewed by the Investigator or a qualified designee for final assessment of eligibility.

The Investigator must review and confirm eligibility prior to randomization. Once all eligibility criteria have been met, the Day 1 visit should be completed as soon as possible.

8.1.1 Informed Consent

An abbreviated prescreening informed consent process may be utilized to conduct initial prescreening (i.e., denoted Tier 1 and Tier 2 per Table 1), if allowed at the investigative site. Prescreening consent does not require the study partner.

Informed consent for the full trial must be obtained prior to performing any Tier 3 and Tier 4 screening procedures per Table 1. Informed consent will also be obtained from a designated study partner prior to the Day 1 visit (not required for the abbreviated prescreening consent). The study partner should be an individual who is in contact with the participant for at least 10 hours each week, and agrees to accompany the participant to study visits, or is available by telephone.

8.1.2 Medical History and Demographics

Medical history includes active conditions, and any medical illnesses, diagnoses, and surgeries considered clinically relevant by the Investigator.

The review will also include a detailed assessment of AD, including:

- date of symptom onset and clinical presentation
- date and method of diagnosis
- · prior and ongoing treatments, surgeries, or therapies
- · prior (or current) participation in interventional clinical trials.

Demographic information (date of birth, sex, race, ethnicity) will be recorded at Screening (as allowed by local regulations).

8.1.3 Phosphorylated tau-217

Participants who meet Tier 1 eligibility criteria, including MMSE, should proceed to Tier 2 (includes plasma pTau217). The time and date of the plasma pTau217 test should be recorded on the Lab Requisition Form. Participants may proceed to Tier 3 screening assessments once evidence of qualifying pTau217 is met.

Plasma phosphorylated tau 217 (pTau217) is a non-invasive diagnostic test shown to accurately predict the likelihood for an individual to have Alzheimer's disease brain amyloid pathology (Ashton, Brum et al. 2024, Therriault, Woo et al. 2024). The incorporation of the plasma pTau217 biomarker in ASN51-201 is intended to identify early AD patients with evidence of brain amyloid pathology, to facilitate trial screening, and to enable the recruitment of diverse participants by avoiding traditional costly and invasive diagnostic AD tests like amyloid beta PET imaging and CSF amyloid testing.

The plasma pTau217 eligibility result is to be reported to the site in the units of pg/mL. If the plasma pTau217 result does not meet criteria for eligibility, the participant is not to complete any additional screening, and will be considered a screen failure.

Further details on the plasma pTau217 assay can be found in the study Laboratory Manual.

8.1.4 Apolipoprotein E Genotyping

Carriers of the apolipoprotein E (APOE) &4 genotype are at an increased risk for developing sporadic late-onset Alzheimer's disease and cerebral amyloid angiopathy. APOE4 also influences the rate of clinical progression of AD. A blood sample will be obtained for APOE genotyping. APOE status may be disclosed to the Investigator and participant.

8.1.5 Height

A standing height will be measured and recorded using a stadiometer.

8.1.6 Virology Screen

Participants will be screened for hepatitis B surface antigen (HbsAg) and hepatitis C antibody.

8.2 Efficacy Assessments

The assessments and procedures to support trial objectives and derive specified efficacy endpoints (Section 3) are briefly described in the following sections. Timing of assessments is summarized in Section 1.3. Consult the Study Reference Manual for more information.

8.2.1 Cognitive and Functional Assessments

Whenever performed on the same day, cognitive and functional assessments should be performed before procedures that may be stressful for participants (e.g., MRI, PET, blood draw, or CSF sampling).

Raters involved in administering the cognitive function assessments will be blinded throughout the trial. To avoid issues with inter-rater variability, efficacy assessments should be administered by the same individual at the investigative site at approximately the same time of day throughout the duration of participation, where possible.

Data obtained from the ADAS-Cog13, MMSE, and CDR-SB will also be used to derive the ADCOMS.

8.2.1.1 Mini-Mental State Exam (Version 2)

The MMSE is a standardized assessment of mental status and evaluates 7 cognitive domains: orientation to time and place; registration and recall of 3 words; attention and calculation; language; and visual construction (Folstein, Folstein et al. 1975). The instrument is widely used as a brief screen of cognitive abilities (Hall, Forjaz et al. 2015). Administration time is approximately 10 minutes. The MMSE is also administered during pre-screening.

8.2.1.2 Alzheimer's Disease Assessment Scale-Cognitive 13

The modified Alzheimer's Disease Assessment Scale (ADAS-Cog 13) (Mohs, Knopman et al. 1997) includes all original ADAS-Cog items and extends the cognitive domains and range of symptom severity without a substantial increase in the time required for administration. The ADAS-Cog13 consists of 13 items that are commonly impaired in Alzheimer's Disease: orientation, verbal memory, language, praxis, delayed free recall, digit cancellation, and maze-completion measures. Scores range from 0 to 85; higher scores indicate greater severity. Administration time is approximately 30 minutes.

8.2.1.3 Clinical Dementia Rating – Sum of Boxes

The Clinical Dementia Rating – Sum of Boxes (CDR-SB) is a 5-point scale to characterize 6 domains of cognitive and functional impairment simultaneously (Coley, Andrieu et al. 2011). The CDR is obtained through semi structured interviews of participants and study partners. The

score is used to characterize and track the level of impairment/dementia. The CDR-SB can be used to accurately stage AD and discriminate between very early AD and those with mild cognitive impairment (O'Bryant, Waring et al. 2008).

8.2.2 Imaging Assessments

Acquiring MRI images in conjunction with ¹⁸F MK-6240 PET is permitted if dual PET/MRI imaging devices are utilized.

8.2.2.1 18F MK-6240 PET Scan

Positron emission tomography (PET) imaging of NFT tangle pathology with the tau tracer MK-6240 is a biomarker method to measure the effect of ASN51 on the progression of AD tau NFT pathology.

Additional information is available in the Imaging Manual.

8.2.2.2 Volumetric Magnetic Resonance Imaging

An MRI will be performed as part of Screening. The MRI scan will be submitted to the central MRI vendor for final determination of eligibility. Results of centrally read MRIs will be used for data analysis and reports; relevant safety and eligibility results will be communicated back to the site. Volumetric MRI will be performed to assess changes in whole brain, ventricular and select region of interest and cortical thickness volumes.

Additional information is available in the Imaging Manual.

8.3 Safety Assessments

Assessments to characterize safety and tolerability of ASN51 are described below; associated safety endpoints and planned analyses are described in Section 3 and Sections 9.2 and 9.6, respectively.

8.3.1 Physical Examination

Complete physical examinations will be performed by the Investigator or designated licensed professional (MD, NP, RN, PA, or equivalent).

A complete physical examination includes general appearance; head, eyes, ears, nose, and throat; and cardiovascular, dermatologic, respiratory, gastrointestinal, musculoskeletal, and neurologic systems (include neurological assessment of cranial nerves, motor, sensation, coordination, reflexes, and gait).

Findings will be recorded as normal/abnormal for each parameter with additional description as indicated.

8.3.1.1 Weight

Weight (measured in kilograms) and height (in meters) will be measured and recorded during each physical examination. Participants may remain in clothes.

8.3.2 Vital Signs

Vital signs include seated systolic and diastolic blood pressure (mm Hg), heart rate (beats per minute), respiration rate (breaths per minute), and temperature (°C). Measurements should be obtained after the participant has been seated for a minimum of 5 minutes, and before any additional assessments are completed.

8.3.3 Electrocardiogram

A routine 12-lead ECG will be performed after the participant has rested for a minimum of 5 minutes in the supine position. All ECGs must be performed and recorded in triplicate. Triplicate ECGs should be taken at approximately 1-minute intervals. Obtain ECGs, to the best of the site and participants' ability, at approximately the same time of day at each visit to minimize diurnal variation.

8.3.3.1 ECG Parameters

ECG Parameters include PR interval, QRS duration, QT interval, and QTcF. ECG administration procedures will be standardized, and results will be read centrally by qualified personnel blinded to treatment assignment, timepoint, and participant data.

ECGs will be transmitted to and interpreted by a central vendor as normal or abnormal, with clinical significance determined by the Investigator.

8.3.4 Clinical Laboratory Assessments

Laboratory assessments will be used routinely to assess eligibility and IMP safety in all participants per Table 1 and Table 2, respectively. After initiation of IMP, clinically significant abnormal laboratory findings must be documented as an AE. Clinical laboratory parameters to be assessed for safety are listed in Section 13.2. The Study Reference Manual provides details on sample collection and processing.

Fasting is not required; fasting status will be recorded.

All laboratory assessments will be conducted by a central laboratory unless otherwise specified.

8.3.4.1 Serum Chemistry

Blood samples will be obtained for serum chemistry parameters (comprehensive metabolic panel) as noted in Section 13.2.

8.3.4.2 Hematology

Blood sample will be obtained for hematology parameters (complete blood count with differential) as noted in Section 13.2.

8.3.4.3 Urinalysis

A urinalysis panel (dipstick with microscopic examination on positives) will be performed with parameters as noted in Section 13.2.

8.3.4.4 Coagulation Panel

A coagulation panel will be performed with parameters as noted in Section 13.2.

8.3.4.5 Serum Hormone Markers

Serum hormone markers will be obtained as outlined in Section 13.2.

8.3.5 Suicidal Ideation and Behavior Risk Monitoring

8.3.5.1 Columbia Suicide Severity Rating Scale

To prospectively assess suicidal ideation and behavior, the C-SSRS will be administered by site personnel. The "Screen Version" questionnaire will be administered at Screening. The "Since Last Visit" questionnaire will be administered at all subsequent visits. Depending on the cognitive state of the participant, some questions within the C-SSRS may be deemed inappropriate by the Investigator and/or site personnel and may be omitted.

Integration of information from other sources (e.g., family, friends, or significant others; study partners or health professionals; hospital or emergency room records) may be evaluated and integrated into the assessment as appropriate.

Responses will be reviewed during the visit; if emergent suicidal ideation or behavior is indicated, the Investigator will promptly evaluate the participant to ensure proper management and participant safety.

8.4 Adverse Events and Serious Adverse Events

Definitions, recording, follow-up, and reporting requirements for AEs and SAEs follow routine pharmacovigilance practice are provided in Section 12.

Trial-specific guidance is provided in the following subsections.

8.4.1 Time Period and Frequency for Collecting Adverse Event Information

All AEs, SAEs, AESI, and partner pregnancies occurring during the protocol-specified timeframes (Table 7) will be assessed and reported per guidelines provided in Section 12.

Table 7 Adverse Event Reporting Periods

Event Type	Reporting Period	Additional Requirements
AE/SAE during Screening Period	Date of participant informed consent through start of Day 1 Visit (prior to first dose of IMP)	Report as AE/SAE only if related to trial-specified procedure (medical history otherwise)
Treatment-emergent AE/SAE	First dose of IMP through 4 weeks post final dose of IMP	Report SAEs outside of reporting period if assessed as related to IMP
AESI	First dose of IMP through 4 weeks post final dose of IMP	Report AESI outside of reporting period if assessed as related to IMP
Pregnancy of partner	Date of participant informed consent through 4 weeks post final dose of IMP	Obtain consent to follow partner pregnancy

AE = adverse event; AESI = adverse event of special interest; IMP = investigational medicinal product; SAE = serious adverse event.

Clinically significant changes from baseline in any safety or clinical laboratory parameter will be recorded as AEs or SAEs, if deemed appropriate by the Investigator.

8.4.2 Identifying Adverse Events and Serious Adverse Events

At each visit, participants will be asked about any new or ongoing AEs since the previous visit. Spontaneous reporting of AEs and SAEs will be encouraged.

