2.2.2 Risk Summary

2.2.2.1 Intervention Risks and Mitigation

2.2.3 Overall Benefit: Risk Conclusion

3 OBJECTIVES AND ENDPOINTS

Objectives	Endpoints							
Primary								
To evaluate the safety and tolerability of daily doses of ASN51 as compared with placebo	Incidence and severity of AEs Changes from baseline in laboratory safety assessments (including clinical chemistry, hematology, urinalysis, and serum hormone markers), Changes from baseline in vital signs, 12-lead electrocardiograms, and physical (including neurological) examinations Changes from baseline in C-SSRS							
Key Secondary								
To evaluate the effect of daily doses of ASN51 as compared with placebo on the pathophysiology of early AD To evaluate the effect of ASN51 versus placebo in change from Baseline to Week 24 on the pathophysiology of early AD	Change from baseline through Week 24 in CSF pTau217 Change from baseline through Week 24 in CSF total tau protein Change from baseline through Week 24 in plasma pTau217							
Other Secondary								
To evaluate the effect of daily doses of ASN51 as compared with placebo on tau pathology in early AD	Change from baseline through Week 24 in MK-6240 tau PET signal							
To evaluate the pharmacokinetics of ASN51 in early AD	Trough (C _{min}) at steady state and maximum (C _{max}) concentration of ASN51 in plasma at steady state through Week 24							
Tertiary/Exploratory								
To evaluate the effect of daily doses of ASN51 as compared with placebo on the pathophysiology of early AD To evaluate the effect of ASN51 versus placebo in change from Baseline to Week 24 on biomarkers of early AD	 Change from baseline through Week 24 in biomarkers, including but not limited to: Plasma Phosphorylated tau 181, GFAP, Aβ42/40, NFL CSF Phosphorylated tau 181, microtubule binding region tau 243, GFAP, Aβ42/40, NFL, neurogranin 							

ct of daily doses of with placebo on in early AD Change from baseline through Week 24 in: CDR-SB score ADAS-Cog13 score MMSE score ADCOMS score						
com Baseline to cructure Change from baseline through Week 24 in volumetric brain MRI parameters (e.g., whole brain volume, lateral ventricular volume, and cortical thickness measures of certain brain regions)						
Extension Period						
-term safety and 1 in early AD The incidence and severity of AEs over the DB placebo-controlled and LTE periods of the study						

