5 POPULATION

5.1 Selection of Trial Population

This trial will be conducted in adults (aged 50 to 80 years) with a diagnosis of early AD. Eligible patients should meet diagnostic criteria for mild cognitive impairment (MCI) due to AD or mild AD dimentia, collectively referred to as early AD. All patients should have a plasma pTau217 concentration above a pre-determined cut-off to confirm the presence of brain amyloid pathology. Mini Mental Status Examination (MMSE) should range between ≥ 20 and ≤ 28 at baseline with a global Clinical Dementia Rating (CDR) score of 0.5 or 1.0. All participants should meet National Institute on Aging and the Alzheimer's Association (NIA-AA) diagnostic criteria for MCI or mild AD (Jack, Bennett et al. 2018) and have a CDR memory box score of 0.5 confirming episodic memory impairment.

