5.3 Inclusion Criteria

To be eligible to participate in this trial, an individual must meet all the following criteria:

- Male or female age 50 to 80 years inclusive at the time of consent.
- Ability of the participant and/or his/her legally authorized representative (e.g., parent, spouse, or legal guardian, where local regulations and institutional practices permit), as appropriate and applicable, to understand the purpose and risks of the study, to provide informed consent, and to authorize the use of confidential health information in accordance with national and local privacy regulations.

- Must consent to APOE genotyping. The participant's APOE status may be disclosed to him/her at the Investigator's discretion.
- 4. Must have a care partner who, in the Investigator's judgment, has frequent and sufficient contact with the participant (at least 10 hours/week) as to be able to provide accurate information about the participant's cognitive and functional abilities. The care partner must agree to accompany the participant to clinic visits and/or be available by telephone at designated times to provide information to the Investigator and study staff about the participant (and to attend in-person clinic visits that require care partner input for scale completion) and must agree to monitor the participant's administration of any prescribed medications. A care partner should be available for the duration of the study, and the participation of the same care partner for the duration of the study is a top priority. The care partner must be literate and provide informed consent.
- A plasma pTau217 result consistent with the presence of amyloid pathology (defined as > 0.18 pg/mL).
- A clinical diagnosis of AD at either the mild cognitive impairment or mild AD dementia stage per NIA-AA criteria (Jack, Bennett et al. 2018), consistent with Stage 3 and Stage 4 in the FDA draft guidance for early AD (FDA draft 2024).
- Gradual and progressive change in cognition for at least 6 months as reported by the participant and study partner.
- Global CDR of 0.5 to 1 (inclusive) and memory box score ≥ 0.5 at Screening.
- MMSE score of 20 to 28 (inclusive).
- Body mass index greater than 18.5 and less than 35 at Screening.

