5.4.1 Exclusion Criteria by Medical History

- Any medical or neurological/neurodegenerative condition (other than AD) that, in the
 opinion of the Investigator, might be a contributing cause to the participant's cognitive
 impairment (e.g., current history of substance abuse, uncontrolled vitamin B12 deficiency or
 abnormal thyroid function, stroke or other cerebrovascular condition, normal pressure
 hydrocephalus, Parkinson's disease, Lewy body dementia, cerebral amyloid angiopathy,
 frontotemporal dementia) or could lead to discontinuation, lack of compliance, interference
 with study assessments, or safety concerns.
- Non-amnestic presentation of AD as judged by the Investigator.
- Woman of childbearing potential (per CTFG 2020).
- Excessive alcohol use (defined as more than 3 alcoholic drinks per day or 21 drinks per week for men and 2 alcoholic drinks per day or 14 drinks per week for women) from the Screening Visit until the end of the Follow-up Period.
- History of cancer in the past 3 years. Exceptions: non-metastatic basal and/or squamous cell
 carcinoma of the skin, in situ cervical cancer, non-progressive prostate cancer, participants
 with cancer in remission > 5 years, or other cancers with low risk of recurrence or spread.
- History of human immunodeficiency virus infection (active or past), or active hepatitis C infection.
- 7. History of liver disease including hepatitis B, hepatitis C, primary biliary cholangitis, primary sclerosing cholangitis, alpha-1 antitrypsin disease, alcoholic liver disease, Wilson's disease, hemochromatosis, portal hypertension, biopsy-proven metabolic associated steatohepatitis, autoimmune hepatitis, drug induced liver disease.
- Clinically significant systemic infection or severe infection (e.g., pneumonia, septicemia) within the 30 days prior to Screening or between Screening and Day -1.
- History of seizures within 10 years prior to Screening Visit 1 or history of epilepsy (except for history of febrile seizures in childhood).
- 10. Presence of clinically significant and/or unstable psychiatric illness, in the Investigator's opinion (e.g., bipolar disorder), within the 6 months prior to Screening Visit 1 and/or a documented prior history of chronic schizophrenia.
- 11. History of major depressive disorder, bipolar disorder, or generalized anxiety disorder with an active episode in the past 5 years.

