9.10 Sample Size Determination

The sample size was not derived statistically, but empirically determined based on the safety objectives of this dose ranging trial. With N = 21 per arm (accounting for a 20% dropout rate), the rule of 3 suggests that the probability of observing at least 1 occurrence of individual AEs is at least 95% if the incidence rate is greater than 1/(N/3), which is approximately 14%.

For the plasma and CSF key secondary biomarker endpoints (CSF pTau217, plasma pTau217, and CSF tTau), the study has 90% power at a one-sided alpha of 0.1 to observe a baseline-adjusted change from baseline of 20% relative to placebo assuming a 25% standard deviation (e.g., Cohen's d of 0.8). A difference of 20% from placebo has been observed for CSF tTau and pTau with the OGA inhibitor Thiamet G in the rTg4510 tau model (Wang, Smith et al. 2018) and is a similar effect size to what has documented after 24-weeks of treatment of early AD patients with amyloid lowering therapies like lecanemab and donanemab (Salloway 2023, van Dyck, Swanson et al. 2023).

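### Section 8.4.2 has staff actively ask only the memory-impaired participant about adverse events, so symptom-type events between visits may be under-counted although a mandatory care partner could also be asked

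*Combined protocol and SAP*

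**What the plan says.** Section 3 lists "Incidence and severity of AEs" first among the primary endpoints. Section 8.4.2 has two sentences on how events are found. The first covers active questioning: "At each visit, participants will be asked about any new or ongoing AEs since the previous visit". The second covers everything unsolicited: "Spontaneous reporting of AEs and SAEs will be encouraged".

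On the population, Section 5.1 says participants should "have a CDR memory box score of 0.5 confirming episodic memory impairment". The list in Section 5.3 sets the memory box at 0.5 or higher. Section 5.4.1 excludes "Non-amnestic presentation of AD as judged by the Investigator".

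On the care partner, criterion 4 in Section 5.3 requires at least 10 hours of contact a week. The partner must come to visits and/or be reachable by telephone "to provide information to the Investigator and study staff about the participant". Section 4.1 also describes the participant as attending with the study partner.

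For one safety instrument, the C-SSRS, Section 8.3.5.1 makes explicit room for other informants: "Integration of information from other sources (e.g., family, friends, or significant others; study partners or health professionals". Section 8.4.2 has no matching sentence.

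**The concern.** The one direct question about AEs goes to the person whose episodic memory is impaired by the entry criteria. The recall interval is mostly 4 weeks, and 6 weeks for the last LTE visits (Tables 2 and 3). The follow-up contact, which closes the treatment-emergent window, may be a telephone call (footnote d of both tables).

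Elsewhere the protocol does not rely on the participant alone. Cognitive change at entry is reported by participant and partner, the CDR interviews both, and the C-SSRS may draw on partners.

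The events at risk are transient symptoms between visits, such as nausea, fatigue, dizziness or a fall, that leave no trace in a laboratory result, ECG or examination. If some go unreported, AE incidence in the tables is too low. Symptom reports also feed some of the liver-related criteria in Section 7.1.1, so the effect need not stop at the tables. Section 9.10 justifies the trial's size by the chance of observing AEs, and that calculation takes capture as complete.

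**Working it through.** **Inputs**

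- N = 21 per arm, incidence of about 14%, probability of at least 95%: Section 9.10.
- 26 randomized per arm: Synopsis. The Safety Analysis Set is everyone given at least one dose: Section 9.1.2. I assume all 26 are dosed.
- Capture probability *s*, the chance that an affected participant's event is recorded: not in the documents. The values below are assumed.

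**Step 1: the plan's own figure.** Section 9.10 states that "the probability of observing at least 1 occurrence of individual AEs is at least 95" percent above the rule-of-3 threshold.

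- Threshold: 3/21 = 0.143.
- Exact probability at 1/7: 1 − (6/7)^21 = 0.961. At 0.14: 1 − 0.86^21 = 0.958.
- Exact incidence giving 95%: 1 − 0.05^(1/21) = 0.133.

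The stated figure reproduces.

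**Step 2: incomplete capture.** If the true incidence is *p*, the recorded incidence is *s·p*, and

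P(at least one recorded) = 1 − (1 − s·p)^n.

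The true incidence needed for 95% is [1 − 0.05^(1/n)]/s. The numerator is 0.1329 for n = 21 and 0.1088 for n = 26. With p = 0.14:

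| s (assumed) | s·p | P, n = 21 | P, n = 26 | Incidence for 95%, n = 21 | Incidence for 95%, n = 26 |
|---|---|---|---|---|---|
| 1.0 | 0.140 | 0.958 | 0.980 | 13.3% | 10.9% |
| 0.9 | 0.126 | 0.941 | 0.970 | 14.8% | 12.1% |
| 0.8 | 0.112 | 0.917 | 0.954 | 16.6% | 13.6% |
| 0.7 | 0.098 | 0.885 | 0.932 | 19.0% | 15.5% |
| 0.5 | 0.070 | 0.782 | 0.848 | 26.6% | 21.8% |

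At 14% incidence, 95% is kept if capture is at least 0.1329/0.14 = 0.95 with n = 21, or 0.1088/0.14 = 0.78 with n = 26. N = 21 ignores the exposure of those who drop out, and n = 26 treats them as fully exposed. The truth lies between.

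**Step 3: comparison with placebo.** With the same *s* in every arm and no false reports, the difference becomes s·p₁ − s·p₀ = s(p₁ − p₀), so it shrinks by the factor *s*. The ratio s·p₁/(s·p₀) = p₁/p₀ does not change.

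**Step 4: which events *s* applies to.** Several routes to an AE need no recall:

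- physical examination changes (Table 2, footnote g);
- ECG findings (Section 7.1.1);
- laboratory findings (Section 8.3.4);
- clinically significant changes in any safety parameter (Section 8.4.1).

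The table above is therefore relevant only to symptom-type events that nobody volunteers.

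**The case against.** The strongest reply is that the gap is narrow.

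- **Other routes to an AE.** Section 8.4.2 encourages spontaneous reporting without limiting who reports. The two specific risks visible in Section 8.4.3, PR prolongation or AV block and liver injury, are followed by ECG and serum chemistry. A reader might infer that AEs come only from participants. The documents do not support that; the restriction applies to active questioning. This part of the reply stands.
- **The partner is not barred.** Criterion 4 gives the partner a general duty to inform staff, wide enough to include AEs. The text is silent rather than prohibitive. This also stands, but silence leaves each site to decide whether to ask, and criterion 4 names only cognitive and functional abilities as the subject of the partner's knowledge.
- **Early disease.** Participants have MMSE 20 to 28 and global CDR 0.5 to 1, and no recall or capture rate is given. A reader might infer that events will certainly be missed, or missed unequally by arm if ASN51 affects cognition. Neither is shown.
- **Size.** The figures depend on assumed *s* and on the choice of N. With 26 dosed per arm, 80% capture still gives 0.95. Section 9.10 says the sample size was set empirically, and safety p-values are descriptive (Section 9.2.2), so no decision rule fails.
- **Unseen text.** The public text breaks off within Section 8.4.3.2 and resumes at Section 8.10, and the Study Reference Manual is not available. An instruction to question the partner may exist there.
- **Follow-up call.** Footnote d provides for an in-clinic visit, if necessary, for participants with an ongoing AE or a history of abnormal ECGs. That helps with known problems but does not bring out forgotten ones.

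**Conclusion.** The point holds for solicited, symptom-type AEs. As written, Section 8.4.2 directs the question to an informant selected for impaired episodic memory and leaves out a better-placed informant whom the protocol already requires. Such events may be under-counted. If capture is equally incomplete across arms, absolute incidences and absolute differences from placebo fall in proportion, while risk ratios are preserved.

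The size cannot be estimated from the documents. The range in the working (at 14% incidence, 0.94 to 0.78 with 21 per arm and 0.97 to 0.85 with 26, for capture from 90% to 50%) is an illustration on assumed values. A reader might take it as showing that the Section 9.10 statement is wrong. It does not: that figure is correct under full capture. Primary safety endpoints based on laboratory tests, ECGs, vital signs and examinations do not depend on recall.

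This is a worthwhile, inexpensive improvement to how a primary endpoint is collected, not a flaw that undermines the trial.

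**What to change.** Amend Section 8.4.2 so that at each visit, including Day 14 and the follow-up contact that may be held by telephone, the participant and the care partner are both asked a standard, non-leading question about new or ongoing AEs since the last visit. If the partner is absent, use the telephone contact that criterion 4 already provides for. Record the source of each report (participant, care partner or both). If the sections not in the public text or the Study Reference Manual already contain such an instruction, align Section 8.4.2 with it.

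The cost is one amended passage, one eCRF field and a few minutes per visit, with no new visit, procedure or staff. Somewhat more minor AEs will be recorded in all arms. The source field would also show how many events only the partner reported, which the documents currently give no means of knowing.
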